Huntington's Disease Young Adult Study 2.0

5th December 2023

HD-YAS 2.0 SAP 5th December 2023

Overview:

The Huntington's Disease Young Adult Study (HD-YAS) is part of the Wellcome Trust funded TREAT-HD programme, which aims to deliver therapies to prevent neurodegeneration in HD. In parallel to exploring novel therapeutic strategies in HD, HD-YAS aims to identify the optimum time window to deliver preventative treatments. Specifically, it seeks to determine early systems-level pathology in very early premanifest HD gene carriers, and to assess the impact of this degeneration on symptomatology. From 2017 to 2019 a cohort of 64 premanifest HD gene carriers approximately 24 years from expected symptom onset and 67 matched controls underwent clinical, cognitive, neuropsychiatric, neuroimaging and biofluid assessments (Scahill *et al*, 2020). There was no evidence of disease-related functional impairment. No significant differences in brain structure and function were evident between gene carriers and controls with the exception of smaller striatal volumes. Neurofilament light (NfL), a marker of neuronal damage, was elevated in gene carriers, with higher levels in those closest to expected symptom onset. HD-YAS 2.0 provides follow up approximately 4.5 years after baseline with the aim of determining whether ongoing longitudinal degeneration is evident and whether this impacts function. We will determine this by addressing the following hypotheses:

Hypothesis 1: There is evidence of a disease-related measurable phenotype ~20 years from expected symptom onset in:

- a) brain imaging;
- b) cognition;
- c) neuropsychiatric function; and
- d) biofluid measures.

Hypothesis 2: There is evidence of disease-related *longitudinal* change ~20 years from expected symptom onset in:

- a) brain imaging;
- b) cognition;

- c) neuropsychiatric function; and
- d) biofluid measures.

Hypothesis 3: Early pathological events lead to impairment in isolated functional domains such as cognitive flexibility.

Hypothesis 4: Individuals with higher levels of somatic CAG-repeat expansion are more vulnerable to early striatal atrophy, breakdown of corticostriatal connections and cortical pathology.

Hypothesis 5: Measures identified as showing disease sensitivity in hypotheses 1 and 2 have utility for future trials of disease-modifying therapy in premanifest HD gene carriers.

The Cohort

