Approximately 4.5 years after baseline 57 premanifest HD gene carriers (89% retention) and 45 healthy controls (67% retention) returned for a follow-up visit (HD-YAS 2.0). An additional 23 new participants were recruited: 9 premanifest HD gene carriers and 14 controls. The full cohort consists of 66 premanifest HD gene carriers and 59 healthy controls, matched for age, gender and education. All participants completed the clinical and cognitive assessments, 91% had MRI and 86% underwent CSF collection. The cohort will be characterised in terms of the new Huntington's Disease Integrated Staging System (HD-ISS) (Tabrizi *et al*, 2022), which incorporates disease pathology and biomarkers within staging classification. In addition, predicted years to clinical onset will be linked to standardisation of the CAG-Age-Product (CAP) score via previously described statistically modelling of CAP=100 at the expected age of diagnosis (Warner *et al*, 2022). These measures will be important for disease staging in future clinical trials.

General Methods

Measures

Approximately 70 individual variables from various measurement domains will be

analysed as outcome variables that may differ between the premanifest HD gene carriers and controls. The majority of measures are identical to baseline, with a few exceptions:

- One cognitive task, the breakpoint assessment, was removed from the battery due to feedback from participants. A novel task, The Goals Prior Assay, was introduced to capture the motivational domain.
- Neurogranin, a marker of synaptic function, was not assessed at this timepoint. There was no significant difference in CSF neurogranin concentration between the premanifest HD gene carrier and control groups at baseline in HD-YAS.
- Total huntingtin (tHTT) was not assessed at this timepoint. At baseline, the presence of the mutant HTT gene did not have any effect on tHTT concentrations; tHTT concentrations in CSF were unchanged in premanifest HD gene carriers.
- Volumetric neuroimaging measures, in addition to cross-sectional measures at this timepoint, include a direct measure of change, the boundary shift integral (BSI). This method has shown greater sensitivity to subtle longitudinal volumetric change than independent volume measures at each timepoint (Freeborough and Fox).
- We have included a measure of CAG-repeat expansion derived from blood DNA. This will be assessed using both the HD-YAS 1.0 and HD-YAS 2.0 samples.

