The complete set of outcome measures are listed by domain in Table 1.

Descriptive statistics: All measures will be summarized by descriptive statistical tables and plots. These will include tables of means, medians, standard deviations, and ranges for the total values and the longitudinal change in values (where applicable). These will be accompanied by box plots or scatter plots as applicable. Tables and plots will divide the data in several ways, including CAG-expanded versus controls, and (within the CAG-expanded) HD ISS stage 1 versus 0, CAP100 score, and CAP100 score ≥ 100 versus < 100 .

Mutant huntingtin assay considerations:

By definition, mutant huntingtin (mHTT) levels should be 0 in bioassays collected from the non-CAG-expanded control group. Consequently, analyses to test mHTT levels associations will be restricted to the CAG-expanded group. To test possible artifacts in

measured mHTT levels, we will repeat this model with hemoglobin (Hb) levels included as an additional candidate covariate.

Somatic expansion assay:

The distribution of CAG lengths in DNA, as measured by polymerase chain reaction (PCR) will be available for the first time for HD-YAS 1.0 as well as HD-YAS 2.0. Somatic expansion lengths measured after PCR are subject to the artifact of PCR slippage, whereby true CAG lengths are occasionally shortened (and very rarely lengthened) due to errors in the chain reaction. This phenomenon is known as PCR slippage. Correction for PCR slippage has been an ongoing area of collaboration between [name] lab and [name]. They have developed statistical methods to approximately correct for the slippage artifacts and generate what is believed to be a more accurate representation of the distribution of expanded CAG lengths. The HD-YAS somatic expansion analyses will be done using two different measures of net somatic expansion. The first of these will be the estimated mean expansion after slippage correction via the above-mentioned method. The second will be the "expansion ratio", which is the measure used in similar published research so far. The expansion ratio is the ratio (before slippage correction) of the proportion of CAG longer than the presumed baseline CAG length divided by the proportion of CAG at that baseline length.

Outliers

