Estimates of sample size requirements will be based upon the estimated longitudinal effect sizes (mean slope divided by between-subject slope standard deviation) calculated from mixed effect longitudinal. The models will be limited to HD gene-expanded participants and follow-up time will be the sole fixed effect. (The resultant estimates of natural history change will thus represent the relevant average natural history progression among the entire group of CAG-expanded participants. Additional effects of potential stratification are discussed shortly below.) Initial calculations will assume 5- and 10-year trials with annual follow-up, 50 and 70% slowing due to treatment, no placebo effect, and use of slopes rather than net change of outcome from the beginning to end of the trials. We will assume no drop-out and that the within-subject outcome variance does not increase over time. These conditions will yield best-case estimates for idealized trials. For any measure, should the resultant sample sizes appear hypothetically feasible, we will perform follow-up calculations assuming 2-, 3-, and 4-year trials with similar and smaller treatment effect sizes.

Potential trial enrichment: For the potential trial outcomes used in the above analyses, we will further test whether the possible stratification criteria of HD-ISS stage of 1 or greater (versus 0) or CAP100 score of 100 or greater are significantly associated with different rates of natural history longitudinal change. We will repeat the sample size analyses described in the previous paragraph with the data limited to the subset of CAG-expanded participants meeting the stratification criterion in question.

Table 1: Outcome variables by modality

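### The CAP100 cut of 100 selects carriers at or past expected diagnosis, so few or no carriers in this far-from-onset premanifest cohort are expected to meet it

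*SAP*

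**What the plan says.** Four parts of the SAP bear on this.

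- **The scale.** The Cohort section links predicted years to clinical onset to a standardised CAP score, obtained by "statistically modelling of CAP=100 at the expected age of diagnosis".
- **The cohort.** The Overview describes "64 premanifest HD gene carriers approximately 24 years from expected symptom onset" at baseline. Hypothesis 1 is framed for follow-up: "There is evidence of a disease-related measurable phenotype ~20 years from expected symptom onset in" four measurement domains. The interval between visits is about 4.5 years.
- **The cut.** Descriptive statistics splits the carriers by "CAP100 score ≥ 100 versus < 100". Potential trial enrichment, under Hypothesis 5, makes the same cut one of two candidate criteria and tests whether a "CAP100 score of 100 or greater are significantly associated with different rates of natural history longitudinal change". The other criterion is HD-ISS stage 1 or greater.
- **The use of the cut.** The sample-size analyses are repeated with the "data limited to the subset of CAG-expanded participants meeting the stratification criterion in question". Those analyses rest on an effect size defined as "mean slope divided by between-subject slope standard deviation".

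Neither document gives another scaling for CAP100, the number of carriers at or above 100, a minimum subset size, a fallback if the subset is empty, or the visit at which CAP100 is taken for the split.

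**The concern.** If the score equals 100 at expected diagnosis and rises with age for a given CAG length, then 100 or greater means that no years remain to expected diagnosis. The study set out to recruit people decades before that point. The definition and the cut do not fit together as written: either the cut is wrong for this cohort, or the scaling is not what the SAP says.

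At stake is the CAP-based half of the enrichment analysis. With no carriers above the cut there is no test and no sample size. With one to three, a number can sometimes be produced, but it carries almost no information and could still be read as advice on enriching a future trial. If the empty stratum is noticed only during analysis, a replacement cut would be chosen with outcome data in view.

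**Working it through.** **Inputs from the documents**

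- Mean years to expected onset at baseline: about 24 (SAP, Overview).
- Interval between visits: about 4.5 years (SAP, Overview).
- Carriers with two visits: 57; new carriers with one visit: 9; total 66 (SAP, The Cohort).
- Limits on who could enter: DBS at or below 240 at baseline (Protocol 3.1), DBS below 240 for new carriers and age 18 to 47 (Protocol 6), and no diagnostic clinical features (Protocol 6, Participant Categories).

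**Assumptions**

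- Years to onset is normally distributed. The documents give no SD, so 7 to 12 years is shown.
- Expected symptom onset (Overview) and expected diagnosis (CAP scale) are treated as the same event. The Cohort section supports this by tying years to onset to the CAP scale.

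**Step 1. The plan's own figure.** 24 − 4.5 = 19.5 years, which matches the SAP's figure of about 20 at follow-up.

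**Step 2. Where a typical carrier sits.** As an illustration, suppose CAP100 is proportional to age at fixed CAG, so that CAP100 = 100 × age / (age + years to onset). At 19.5 years from onset:

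- age 18: 100 × 18 / 37.5 = 48
- age 34: 100 × 34 / 53.5 = 64
- age 47: 100 × 47 / 66.5 = 71

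At only 5 years from onset, ages 18 and 47 still give 78 and 90.

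**Step 3. Expected number at or above 100.** A score of 100 or more needs years to onset ≤ 0, so the expected count among the 57 carriers is 57 × Φ(−mean / SD).

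| SD (years) | HD-YAS 2.0 visit, mean 19.5 | Baseline, mean 24 |
|---|---|---|
| 7 | 0.15 | 0.02 |
| 8 | 0.42 | 0.08 |
| 10 | 1.46 | 0.47 |
| 12 | 2.97 | 1.30 |

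At the 2.0 visit, the chance that none of the 57 qualifies, (1 − p)^57 with p = Φ(−19.5 / SD), is 86% at SD 7, 66% at SD 8 and 23% at SD 10.

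**Step 4. Spread needed for a usable subset.** For 10 of 57 at the 2.0 visit, SD = −19.5 / Φ⁻¹(10/57) = 19.5 / 0.933 = 20.9 years, which is larger than the mean.

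**Step 5. What a subset of three would give.** This is the top of the range in Step 3. Each carrier's slope is treated as observed and normal, and error in the mean slope is ignored.

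- The 95% interval for the slope variance, as a multiple of its estimate, runs from (n − 1)/χ²(0.975) to (n − 1)/χ²(0.025) on n − 1 degrees of freedom. For n = 3 it is 0.27 to 39.5; for n = 28 it is 0.63 to 1.85. Required sample size is proportional to this variance.
- The smallest difference in rate detectable with 80% power at two-sided 5% (noncentral t) is 1.69 between-subject SD for 3 against 54, and 0.76 for 28 against 29.

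**The case against.** The contradiction between the scale and the cut has no answer in the documents. The objections concern its size and the remedy.

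- **The three-carrier figures are an edge case.** They need the widest assumed SD and CAP100 taken at the 2.0 visit. This is right. For SD 7 to 10 the expected count is 0.15 to 1.5, where a slope SD cannot be usefully estimated at all. Step 5 therefore shows the better end of the range, not the expected loss.
- **Baseline is the natural visit for the longitudinal test.** The SAP holds age at its baseline value in the longitudinal models, and CAP is built from CAG and age. This is a fair reading, although the enrichment paragraph does not state it. It lowers the counts to 0.02 to 1.3.
- **The exact scaling lies in a cited source.** A loosely worded definition is as possible as a wrong cut. This stands, and is why the first request is to reconcile the two. Either way the text needs correcting.
- **The normal curve is a guess.** True, but the entry limits work against a heavy tail. Protocol 8 treats the highest disease burden as closest to expected onset, so the DBS limits remove carriers nearest the cut at entry. Premanifest status does not rule out someone past their expected age of diagnosis, so the claim is few or no carriers, not none.
- **Continuous CAP analyses are partly planned.** Protocol 8 includes CAP correlations, and the SAP lists CAP100 as a descriptive breakdown. Neither is the enrichment test of differing rates of change.
- **A cohort median is not a natural enrichment criterion.** Agreed in part. It is one example of a workable cut; a stated external threshold would be better if the sponsor has one.

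**Conclusion.** The concern holds. By the SAP's own definition the cut marks expected diagnosis, and the cohort sits about 20 years short of it on average. Between 0.15 and 3.0 of the 57 carriers with two visits would be expected to qualify at the 2.0 visit, or 0.02 to 1.3 at baseline, for an assumed SD of 7 to 12 years. These are expectations, not counts, and they rest on the normality assumption and on treating onset and diagnosis as one event. A usable subset would need a spread far outside that range.

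The damage is confined to the dichotomous CAP100 test, its subset sample-size rerun and one descriptive split. The HD-ISS criterion, the all-carrier sample sizes and the continuous CAG, age and CAG-by-age terms with follow-up time are untouched. This should be fixed before analysis; it does not threaten the study's main results.

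**What to change.** Reconcile The Cohort, Descriptive statistics and Potential trial enrichment sections of the SAP as follows.

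1. Count the carriers at or above 100 from CAG and age alone, before any outcome modelling, and state which visit's CAP100 is used.
2. Make the CAP enrichment test the interaction of continuous CAP100 at first study visit with follow-up time, among carriers. For BSI outcomes, which are already rates, use the CAP100 main effect.
3. For the subset sample sizes and the descriptive split, state the intended threshold or scaling if 100 is a slip. Otherwise use a cut inside the cohort's range, fixed before outcome modelling. The carriers' median CAP100 at first study visit is one option; it is also defined for the 9 carriers who joined at HD-YAS 2.0, although they contribute no individual slope.
4. Report the number of carriers and a confidence interval with every subset sample size.

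The cost is SAP wording. CAP100 is already to be derived, and the continuous term is a one-parameter summary of effects the longitudinal model already fits. The drawback is that a cut taken from this cohort transfers less readily to other trials than an external threshold, which the continuous analysis only partly offsets.
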